**Visit 6 (Week 12 ± 5d – End of treatment)**

This visit will take place at UPMC Montefiore. Subjects will be asked to fast a minimum of 12 hours to perform the assessments listed below. The visit will last approximately 6 hours.

- Brief physical exam with a body weight measurement and WHO Functional class assessment
- Vital signs (temperature, blood pressure, respiratory rate, heart rate, and pulse oximetry measurements are taken).
- ECG
- Clinical laboratory tests and urinalysis (fasting glucose, comprehensive metabolic panel, fasting lipid profile, CBC/Diff/Plt, uric acid, PT/INR, hemoglobin A1c (this test is performed if subject has abnormal HbA1c))
- Research blood samples for biomarkers, cytokines measurements, NT-proBNP
- Oral (saliva, tongue scraping) and stool samples for microbiome analysis; subjects may be provided a stool collection kit and return the sample in a pre-paid envelope by USPS mail.
- Urine pregnancy test for female child-bearing potential
- IVGTT
- Health related quality of life questionnaire - Pulmonary Arterial Hypertension-Symptoms and Impact (PAH-SYMPACT®)
- Return accelerometer for data download
- Concomitant medications assessment
- AE assessment

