
**END OF TREATMENT: All end of treatment study procedures will take place over 3 visits and can be completed in any order to accommodate scheduling needs.**

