**Visit 7 (Week 12– End of Treatment)**

Subjects will report to the clinic on the morning of Week 12 after a minimum 8-hour overnight fast. Subjects should not take their study medication that morning, prior to arriving at the clinic for their pre-dose assessment.

- Brief physical exam
- Echocardiogram (may be completed on a separate day if a scheduling conflict occurs)
- RHC. Pulse oximetry and automated blood pressures will be measured at regular intervals.
- Hemodynamic measures such as pulmonary vascular resistance (PVR), mean pulmonary artery pressure (mPAP) and left and right ventricular filling pressures, will be measured at baseline and 30 minutes post drug dose and CXA 10 metabolites will be measured with pharmacokinetics sampling time points at baseline and 4-6 hours post drug dose. Food will be given prior to dosing. Research blood samples for biomarkers, cytokines measurements (samples collected at the same times as PK samples)
- Concomitant medications assessment
- AE assessment

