Clinical Laboratory Tests: Clinical lab tests evaluation will include fasting glucose, comprehensive metabolic panel, fasting lipid profile, complete blood count, platelet and differential, and uric acid. In addition, HbA1C levels will be collected at Screening (Visit 1) on all subjects. Subjects with abnormal HbA1C at screening, will have blood collected for HbA1C levels at the end of the treatment period (Visit 6). PT/INR will be evaluated on all subjects as this is standard of care for anyone having a RHC. Patients who are on warfarin will return approximately one week after starting study drug to re-check PT/INR (Visit 3a).

Pulmonary Function Test (PFT): PFTs must be completed no more than 12 months before Screening or at Screening if outside the 12-month window. FEV1 and FVC parameters will be collected to determine eligibility to participate in the trial. Pulmonary function testing will be performed as per clinical standard of care.

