### **Efficacy Assessments**

Right Heart Catheterization (RHC): RHC is performed routinely as a clinical standard of care procedure for diagnostic purposes in this population. RHC will be performed at Screening and at the end of the treatment (Visit 6 – Week 12).

Briefly, RHC will be performed with a balloon tipped, flow-directed, pulmonary artery catheter (e.g. 7F Swan Ganz catheter) inserted through a sheath in the internal jugular vein under continuous

ECG monitoring. An alternate vein may be used at the physician's discretion. All measurements will be recorded with the subject in a supine position, at rest, breathing room air or with supplementary oxygen to obtain peripheral saturations above 90%. Hemodynamic recording of right atrial, right ventricular, pulmonary artery pressures, pulmonary artery wedge pressure and cardiac output will be made. Parameters for analysis will include: Mean RAP, RVSP, RVDP, PASP, PADP, Mean PAP, Mean PAWP, Thermodilution Cardiac Output, PVR, Cardiac Index, and Pulmonary Vascular Compliance. Mixed venous oxygen saturation (SvO2) will be determined from a sample drawn from the Swan-Ganz catheter. Other parameters may be obtained as data permit.

**Echocardiogram:** Noninvasive transthoracic echocardiograms will be completed to assess RV function by measures such as tricuspid annular plane systolic excursion (TAPSE) as well as tissue Doppler of the lateral tricuspid valve anulus (S').

**Six Minute Walk Distance Test and Borg Dyspnea Scale:** The 6MWD test will be performed according to a protocol-specific modification of the American Thoracic Society guidelines. The 6MWD test measures the distance an individual is able to walk over a total of six minutes on a hard, flat surface. The Borg Scale is a method of rating perceived exertion during exercise. It should be performed immediately after the 6MWD test.

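### The Week 12 visits have no fixed order, so PAH-SYMPACT and WHO class can be recorded after the Week 12 catheterization result is known

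*Combined protocol and SAP*

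**What the plan says.** The note on end-of-treatment procedures in section 2.2.2, just before Visit 6, reads "All end of treatment study procedures will take place over 3 visits and can be completed in any order to accommodate scheduling needs".

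The Visit 6 list contains "Health related quality of life questionnaire - Pulmonary Arterial Hypertension-Symptoms and Impact (PAH-SYMPACT" and "Brief physical exam with a body weight measurement and WHO Functional class assessment". The Visit 7 list contains "RHC. Pulse oximetry and automated blood pressures will be measured at regular intervals" and includes neither the questionnaire nor the WHO class. Visit 8 includes neither as well.

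Section 2.2.3, Efficacy Assessments, places the catheterization differently: "RHC will be performed at Screening and at the end of the treatment (Visit 6 – Week 12".

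On coagulation testing, section 2.2.3, Safety Assessments, says "PT/INR will be evaluated on all subjects as this is standard of care for anyone having a RHC". The Visit 6 laboratory list includes "uric acid, PT/INR, hemoglobin A1c (this test is performed if subject has abnormal HbA1c", and the Visit 7 list has no PT/INR.

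**The concern.** PAH-SYMPACT is self-reported and WHO class is a judgment. Either can be colored by knowing how the treatment turned out. The Week 12 RHC supplies that knowledge, because PVR is the main efficacy measure and its 12-week change is the result that subject and study team are waiting for. The section on the open-label period adds interest in the answer: it says the extension is mainly meant for patients who responded during the trial.

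With one arm, no control group shares and cancels a shift of this kind. If some subjects are assessed before the RHC and others after it, the Week 12 values are also collected under mixed conditions. What is at stake is the reading of two secondary endpoints. One of them, health-related quality of life, is named in the study hypothesis.

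**Working it through.** The plan gives no figure on this point and none can be derived, so the check sets the sections side by side.

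1. **Order.** The end-of-treatment note allows any order, and no other section restricts it. Visit 6 has a window of ± 5 days. The text gives Visits 7 and 8 no window and sets no gap between the three. Three visits can be arranged in 3 × 2 × 1 = 6 orders, and by symmetry Visit 7 precedes Visit 6 in 3 of them. This shows what is allowed, not how often it would happen.

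2. **Where the two measures sit.** PAH-SYMPACT and WHO class appear at Visit 6 and at no other Week 12 visit. Appendix A, as extracted, agrees. Each has one Week 12 value, with no second reading to fall back on.

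3. **Where the RHC sits.** The visit list says Visit 7; Efficacy Assessments says Visit 6. The point survives either reading. If Visit 7 is meant, it may come before Visit 6. If Visit 6 is meant, the note still leaves the order of procedures free.

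4. **Who knows what.** Section 2.1 describes a one-arm, open-label study. No section withholds the RHC result from the subject or from the person who rates WHO class. No section says either is told. The exposure is permitted, not certain.

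5. **Use in the analysis.** Section 2.4 lists change from baseline at 12 weeks in PAH-SYMPACT and in WHO class as secondary endpoints. Section 2.5.2 makes the comparison of Week 12 with baseline the primary analysis, which uses exactly the value that is exposed.

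6. **What is not exposed.** Both measures are also taken at Visits 4 and 5 (Weeks 4 and 8), before any end-of-treatment RHC. Treatment-emergent adverse events and PVR rest on neither measure. Under section 6.4.8, subjects who stop drug before Week 10 have no end-of-treatment RHC.

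7. **Baseline order.** PAH-SYMPACT is first recorded at Visit 2. The qualifying RHC comes earlier, at screening or within the preceding 2 months. In the first 10 subjects the screening RHC includes a reading 30 minutes after a dose. No baseline catheterization can show a 12-week change.

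8. **PT/INR.** The Visit 6 text lists it. In the extracted Appendix A the Week 12 mark falls in the same column as the RHC, Visit 7. That column also holds HbA1c (Visit 6 in the text) and the walk test (Visit 8 in the text), so it may be misaligned and needs checking against the original table.

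**The case against.** The strongest objection is that the baseline questionnaire already follows a catheterization. Putting the Week 12 one before the RHC would then create a mismatch in a change score. This stands in part: if undergoing the procedure itself affects self-report, the sequence would differ from baseline. The documents offer no evidence that it does. The concern here is knowledge of the on-treatment result, which no baseline RHC can supply. Withholding the result until both measures are recorded meets the concern without relying on sequence.

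Second, Weeks 4 and 8 are clean, and section 2.5.2 also plans a mixed model over the 12 weeks. That is a useful check, but it does not protect the paired Week 12 comparison.

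Third, nobody is said to disclose the result, and news of PVR can be good or bad. Both are true, and they limit the claim.

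A reader might infer three stronger things that the documents do not support:

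- **A calculable false-positive rate.** This would need a uniform favorable shift in all subjects. The documents give no size, no direction and no proportion affected.
- **Distorted blood markers.** NT-proBNP is a laboratory assay and cannot respond to knowledge of PVR. Cytokines have their own pre-dose draws at Visits 7 and 8, and Table 1 designates Visit 8 for the Week 12 PK/PD samples. No interval between the RHC and the Visit 6 draw is stated.
- **A breached rule on INR timing.** Safety Assessments gives a reason for testing but sets no visit or deadline, so it does not contradict the free visit order.

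**Conclusion.** The concern holds in a limited form. As written, the single Week 12 PAH-SYMPACT and the single Week 12 WHO class can be recorded when the subject or rater already knows the Week 12 PVR result, and the order may vary between subjects. This is a permitted weakness in two secondary endpoints of an uncontrolled, open-label trial. It is not a demonstrated bias: its size and direction are unknown. It would matter only if some subjects have the RHC first and the result is disclosed before these measures are recorded. The primary endpoint, PVR and the sample size are untouched. The point is worth making because the protection costs almost nothing.

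The conflict over the Week 12 RHC visit is plain in the text. The PT/INR discrepancy depends on the original layout of Appendix A.

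**What to change.** Amend the end-of-treatment note in section 2.2.2 so that:

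- the Week 12 PAH-SYMPACT and WHO class are recorded before the Week 12 RHC, or on the RHC day before the procedure;
- where that is not possible, both are recorded before the RHC result is told to the subject or to the person rating WHO class;
- the actual order and dates of Visits 6, 7 and 8 are recorded for every subject;
- all other Week 12 procedures stay flexible.

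Separately, reconcile the Visit 6 list, the Visit 7 list, Efficacy Assessments in section 2.2.3 and Appendix A on when the Week 12 RHC and PT/INR take place, in light of the purpose that Safety Assessments gives for PT/INR. The choice of visit is for the investigators; no rule on INR timing is proposed here.

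The cost is protocol wording and slightly less scheduling freedom at Week 12. No extra visit, test or staff is needed.

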**Visit 7 (Week 12– End of Treatment)**

Subjects will report to the clinic on the morning of Week 12 after a minimum 8-hour overnight fast. Subjects should not take their study medication that morning, prior to arriving at the clinic for their pre-dose assessment.

- Brief physical exam
- Echocardiogram (may be completed on a separate day if a scheduling conflict occurs)
- RHC. Pulse oximetry and automated blood pressures will be measured at regular intervals.
- Hemodynamic measures such as pulmonary vascular resistance (PVR), mean pulmonary artery pressure (mPAP) and left and right ventricular filling pressures, will be measured at baseline and 30 minutes post drug dose and CXA 10 metabolites will be measured with pharmacokinetics sampling time points at baseline and 4-6 hours post drug dose. Food will be given prior to dosing. Research blood samples for biomarkers, cytokines measurements (samples collected at the same times as PK samples)
- Concomitant medications assessment
- AE assessment

**Visit 8 (Week 12 – End of treatment)**

This visit will take place at UPMC Montefiore and the visit will last up to about 7 hours. The subject does not need to fast.

- 6MWT
- Blood draw for Population PK sampling (pre-dose and 4-6 hours after taking the study drug) Subjects will be instructed to take the study medication at the clinic after a breakfast/morning snack containing up to approximately 30% fat
- Research blood samples for biomarkers, cytokines measurements (samples collected at the same times as PK samples)
- Concomitant medications assessment
- AE assessment
- Dispense 1st month of open label CXA-10 after the completion of all end of treatment testing (optional)

Following the completion of all end of treatment assessments, patients have the option to discontinue treatment and have a safety follow up at Visit 9 or patients may also choose to enter the open label extension for 6 months. If patients are in the open label extension, Visit 9 will be the month 1 follow up. If patients wish to enter the open label extension, the first month supply will be dispensed at the end of their final visit for end of treatment testing.

**Telephone Assessments**

**Visit 3b (Week 2; ± 5d), Visit 4a (Week 6; ± 5d) and Visit 5a (Week 10; ± 5d)**

The study personnel will contact the subject by telephone to perform a safety evaluation and review concomitant medications approximately 2 weeks after Visit 3, Visit 4 and Visit 5. The subject will be asked if there were any changes to their concomitant medications. Subjects will also be reminded to bring any remaining medication to their next clinic visit.

**Visit 9 (Week 16; - ± 5d– Follow-Up Visit)**

Visit 9 will take place approximately 4 weeks after the end of treatment. Subjects will report to the clinic on the morning of Week 16 after a minimum 8-hour overnight fast.

- Brief physical exam
- Body weight
- Vital signs (temperature, blood pressure, respiratory rate, heart rate, and pulse oximetry measurements are taken).
- Clinical laboratory testing (fasting glucose, comprehensive metabolic panel, fasting lipid profile, CBC/Diff/Plt, uric acid)
- Research blood samples for biomarkers, cytokines measurements
- Urinalysis
- NT Pro-BNP
- Urine pregnancy test in women of childbearing potential
- 6MWT with Borg Dyspnea Scale
- WHO Functional Class assessment
- Concomitant medications assessment
- AE assessment
- Dispense 2nd month of open label CXA-10 (optional)

### **Open Label Period**

Upon completion of the end of treatment visits, subjects will be given the option to receive open-label drug for 6 months. Subjects will be asked to return for in person visits at month 4 and month 6 for vital signs (temperature, blood pressure, respiratory rate, heart rate, and pulse oximetry measurements are taken), WHO Functional Class assessment, completion of the PAH-SYMPACT questionnaire, a six-minute walk test, a blood collection to measure NT-proBNP level, research samples for biomarkers, cytokines measurements, clinical laboratory testing (fasting glucose, comprehensive metabolic panel, fasting lipid profile, CBC/Diff/Plt, uric acid) and dispense study medication. The total amount of blood drawn is 30ml. Months 3 and 5 will be telephone assessments to perform a safety evaluation and review concomitant medications.

To date, current therapies for pulmonary arterial hypertension (PAH) are vasodilatory and reduce the symptoms associated with pulmonary artery (PA) vasoconstriction. The ability to modify the underlying disease is the most important treatment goal for the next generation of therapies, ultimately translating to better outcomes. CXA-10 has the potential to be differentiating as a “disease modifying” therapy in PAH. The main purpose of the open label period is to provide specific treatment to those patients that have a response during the trial. This can also be a benefit to the patients if they are getting relief from their symptoms from the CXA-10. It will also provide longer term safety data. Patient reported outcomes such as QOL are collected.

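### In the 6-month open-label extension no pregnancy test is scheduled after month 1, leaving about 5 months on CXA-10 untested although a positive test requires withdrawal

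*Combined protocol and SAP*

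**What the plan says.** On completing the end-of-treatment visits, "subjects will be given the option to receive open-label drug for 6 months" (section 2.2.2, Open Label Period). The Visit 8 text fixes where Visit 9 falls in this period: "If patients are in the open label extension, Visit 9 will be the month 1 follow up". Visit 9, at Week 16, lists a "Urine pregnancy test in women of childbearing potential".

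For the time after Visit 9 the Open Label Period text reads: "Subjects will be asked to return for in person visits at month 4 and month 6". Months 3 and 5 are telephone safety contacts. The in-person visits are itemised: vital signs, WHO class, PAH-SYMPACT, six-minute walk, NT-proBNP, research samples, and then "clinical laboratory testing (fasting glucose, comprehensive metabolic panel, fasting lipid profile, CBC/Diff/Plt, uric acid) and dispense study medication". No pregnancy test appears. The general definition of the laboratory panel in section 2.2.3 does not contain one either: "Clinical lab tests evaluation will include fasting glucose, comprehensive metabolic panel, fasting lipid profile, complete blood count, platelet and differential, and uric acid".

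In the main study the urine test has its own line at Visits 1, 2, 4, 5, 6 and 9, and its own row in Appendix A. Appendix A has no columns beyond Visit 9.

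Two other sections bear on this. Section 6.4.8 lists a positive pregnancy test among the reasons for which a subject must be withdrawn. Section 6.1 (Reproductive Risks) states that it is unknown whether the drug can affect an unborn baby, advises contraception, and asks subjects to report a pregnancy.

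**The concern.** A mandatory withdrawal rule that depends on a test works only if the test is done. In the main study it is done about every 4 weeks. In the extension, followed as itemised, it is not done again after month 1 while drug continues to month 6. The month 4 and month 6 visits are described in enough detail, down to the components of the laboratory panel, that the omission cannot be taken as shorthand. Nor can the test be read into the laboratory panel, because elsewhere the protocol always lists it separately.

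What is at stake is the safety of women of childbearing potential who choose the extension: an undetected pregnancy could be exposed to a drug of unknown fetal risk for longer than the main-study schedule would allow.

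**Working it through.** **Inputs**
- The extension starts at the end of treatment, taken as Week 12, and lasts 6 months (section 2.2.2, Open Label Period).
- Visit 9 is at Week 16 ± 5 days, is extension month 1, and has the last listed test (section 2.2.2, Visits 8 and 9).
- Main-study tests from baseline fall at Weeks 0, 4, 8, 12 and 16 (Visits 2, 4, 5, 6 and 9).
- Assumption: one month is 365.25 / 12 / 7 = 4.35 weeks. The protocol does not define a month.

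**Main-study interval**

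Differences between Weeks 0, 4, 8, 12 and 16 are 4, 4, 4 and 4 weeks.

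**Untested time on drug in the extension**
- End of drug: 12 + 6 × 4.35 = Week 38.1.
- Time after the last test: 38.1 − 16 = 22.1 weeks, and 22.1 / 4.35 = 5.1 months.
- With Visit 9 five days late or early (5 / 7 = 0.7 week), the range is 21.4 to 22.8 weeks, or 4.9 to 5.2 months.
- If a month means 4 weeks: 12 + 24 − 16 = 20 weeks.

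On any of these readings the untested time exceeds the whole 12-week main treatment period, and it is 5 or more times the main-study interval (20 / 4 = 5.0; 22.1 / 4 = 5.5). The figure rests only on the 6-month duration and on Visit 9 being month 1.

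**Possible later test**

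Section 2.2.1 asks all subjects to return 4 weeks after stopping study drug. If that applies after the extension, and uses the Visit 9 items, the next test is at about Week 38.1 + 4 = 42.1. That is 42.1 − 16 = 26.1 weeks (6 months) after the last one, and after drug has stopped.

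**After the change proposed below** (months counted from the start of the extension)
- Tests at months 1, 4 and 6: gaps of 3 and 2 months, so the longest is 3.
- With home tests at months 3 and 5 as well: gaps of 2, 1, 1 and 1 months, so the longest is 2.

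**The case against.** The best case on the other side is that protection does not disappear.
- Women who are pregnant, breastfeeding or trying to conceive are excluded at entry (section 3.3).
- Section 6.1 gives contraception advice and asks for prompt self-report.
- The month 3 and month 5 calls are safety evaluations at which a pregnancy could be raised.
- The extension is optional, and the number of women of childbearing potential who would enter it is not given and may be small.

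All of this stands, and a reader who inferred that the extension has no pregnancy safeguard would be going too far. But none of these is a scheduled test, and the section 6.4.8 rule is triggered by a test.

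Two other stronger readings are tempting. The first is that the main study tests at every dispensing and the extension breaks that pattern. It does not test at every dispensing: Visits 3 and 8 list dispensing without a test at the same visit, and rely on Visits 2 and 6. The comparison that holds is the interval between tests.

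The second is that extension subjects have no defined safety follow-up, because section 6.4.8 calls the follow-up Visit 9 and the Visit 8 text has already used that number for month 1. The section 2.2.1 rule is tied to stopping drug, not to Week 16, so it can be applied after the extension as written. The numbering is a matter of wording.

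It is also fair to say that a month 6 test, if drug ends there, cannot shorten exposure any more than a follow-up test can. Its value is as a check before any further dispensing, or as a dated end-of-drug result. The month 4 test, and any home tests during treatment, are the ones that can trigger withdrawal while drug remains to be taken.

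**Conclusion.** The point holds, limited to the testing interval. Women of childbearing potential in the extension have about 5 months on CXA-10 (about 22 weeks; 20 if months are 4 weeks) with no scheduled pregnancy test, against about 4 weeks between tests in the main study. For that time the mandatory withdrawal rule has no scheduled trigger.

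This assumes that the visits are carried out as itemised and that the extension runs its full 6 months from Week 12. A subject who stops early has a shorter gap. The documents do not say how many women this concerns.

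It is a participant-safety gap that should be closed. It does not affect the primary safety endpoint, the PVR analysis or any other 12-week result. The documents do not support the wider inferences that pregnancy cover is absent altogether or that post-extension follow-up is missing.

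**What to change.** In section 2.2.2, Open Label Period, add a urine pregnancy test for women of childbearing potential:
- at month 4, before drug is dispensed;
- at month 6, before any dispensing, or as an end-of-drug test if none is dispensed;
- to approach the main-study interval, as home urine tests reported at the existing month 3 and month 5 calls.

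Add these to Appendix A in columns for the extension.

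The cost is two clinic urine tests and up to two home tests per woman of childbearing potential in the extension (2 + 2 = 4 at most), at contacts that already exist. The two clinic tests alone cut the longest on-drug interval from about 5 months to 3; the home tests cut it to 2. Neither restores strict 4-weekly testing.

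As a wording note only, state that the section 2.2.1 safety follow-up takes place 4 weeks after the last extension dose for subjects who enter the extension.
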